9.3 Inferential statistics

Bivariable associations between key outcomes of interest (HIV/HCV/syphilis prevalence, HIV recent infection, HIV treatment cascade indicators, HIV knowledge, etc.) and predictors of interest may be analyzed using Pearson’s chi-square test for categorical variables (or Fischer’s test for variables with low counts), Student’s t-test for normally distributed continuous variables, and non-parametric tests for non-normally distributed variables (Kruskal-Wallis or Wilcoxon).

Multivariable analysis may be used to test the associations of key outcomes with independent variables that were significant in bivariable analysis. Logistic regression may be used for categorical

outcomes and linear regression for continuous outcomes.

9.4 Trend analysis

To analyze the changes in key outcomes of interest across rounds, the final dataset may be merged with datasets from previous rounds. Only cities that participated in each analyzed round will be included. Combined weights (a product of RDS weight and city sample size weight OR the city population size, when becomes available) will be calculated and applied in the trend analyses. The significance of trend will be tested using two methods: (a) Mantel-Haenszel test of trend, used in the previous studies¹³, and (b) regression models with the survey round as an ordinal independent variable. Additionally, comparison between two consecutive rounds using Pearson's chi-square tests.

9.5 Estimation of HIV incidence

The biological component of the IBBS will provide estimates of recent HIV infection and viral load, to be used for calculation of HIV incidence among PWID.

A new method for calculating annual incidence¹⁴ will be used. The corresponding method was implemented in the package "inctools" (version 1.0.15) for R. This approach has been previously reviewed and approved by international experts and statistics specialists.

The report on the IBBS findings will include a median incidence estimation and interquartile range observed in different cities among PWID, allowing for understanding the variability across the different regions of the country.

9.6 Treatment cascade indicators among PWID living with HIV

HIV treatment cascade calculation will include the following indicators:

Cascade indicator	Calculation
PWID living with HIV	The latest available PWID population size estimate will be multiplied by the prevalence of HIV among PWID according to the IBBS 2023 data
Know about their HIV-positive status	The proportion of PWID who self-reported their HIV-positive status during survey (among those who received HIV-positive rapid test result upon survey and agreed to answer questions about their experience of previous HIV-testing). This calculation will be cross-checked with the healthcare worker's forms.
Registered in the HIV clinic	The proportion of PWID who self-reported to be officially registered in the HIV clinic as HIV-positive (among those who received HIV-positive rapid test result upon survey and agreed to answer questions about their experience of previous HIV-testing). This calculation will be checked through the healthcare worker's form.
Receive ART	The proportion of PWID who self-reported receiving ART (among those who received HIV-positive rapid test result upon survey and agreed to answer questions about their experience of previous HIV-testing).

¹³ Dumchev, K., Sazonova, Y., Salyuk, T., & Varetska, O. (2018). Trends in HIV prevalence among people injecting drugs, men having sex with men, and female sex workers in Ukraine. *Int J STD AIDS*, 29(13), 1337-1344.
doi:10.1177/0956462418784096

¹⁴ Kassanjee R, McWalter TA, Bärnighausen T, Welte A. A new general biomarker-based incidence estimator. *Epidemiology*. 2012 Sep;23(5):721-8. doi: 10.1097/EDE.0b013e3182576c07.

	testing). This calculation will be checked through the healthcare worker's form.
HIV viral suppression	Results of viral load testing carried out at the stage of laboratory analysis.

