4.3 Selection of sites

Available recommendations suggest to perform sample size calculation based on indicators with lowest effective sample size (e.g., viral suppression, where effective sample is limited to the HIV positive fraction). However, with the desired level of precision (e.g. less than +/-10%) at the city level, this yields sample sizes which are not feasible, especially in the cities with low HIV prevalence (e.g. Kharkiv). Therefore, it was recommended to consider clustering of cities based on analyses of trends/similarities to ensure a larger sample size.⁹

Prior to 2020, the IBBS in Ukraine were conducted in each administrative unit (N=27), presumably generating a nationally-representative sample, enabling direct comparison of indicators across rounds and analysis of trends.¹⁰ After the resources for surveillance became more limited, the number of participating cities was decreased to 12 in 2020. The selection of cities was made by the national working group, based on epidemiologic and programmatic priorities. Nevertheless, a direct comparison between 2020 and previous rounds is not possible due to the difference in geography and varying sample sizes in cities that participated in each round.

Considering that accurate monitoring of trends in key indicators in IBBS series is at least as important as point estimates, and also following the CDC recommendation (to cluster cities), it is proposed that *a single cluster of cities will be selected for this round and will remain stable* in the next rounds of IBBS. This strategic approach also corresponds to the concept of sentinel surveillance, in which a consistent sample of sites continues to generate data over an extended period of time. As the sentinel

⁹ CDC/DGHT Key Population Surveillance Team and CDC Ukraine Joint Evaluation of IBBS in Ukraine – Nov. 2017

¹⁰ Dumchev, K., Sazonova, Y., Salyuk, T., & Varetska, O. (2018). Trends in HIV prevalence among people injecting drugs, men having sex with men, and female sex workers in Ukraine. *Int J STD AIDS*, 29(13), 1337-1344.

doi:10.1177/0956462418784096

approach implies, selected sites should represent geographically and epidemiologically diverse areas and be most likely to detect emerging behavioral and epidemiologic trends. Given that, the following cities were selected by the national IBBS working group as **sentinel** sites for the 2023 and future rounds of PWID IBBS in Ukraine:

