8.6 Blood collection and DBS preparation

DBS samples are produced from EDTA capillary blood samples for each survey participant with positive results of the third HIV rapid test, and for 10% participants with HIV-negative result of the first rapid test, selected randomly in each city of survey, as well as for those participants who stated they are receiving ART in their questionnaires (Annex 23. DBS registration form).

One Whatman 903 Protein Saver Card (EU) DBS card should be filled with at least with 75 µl of blood

per circle. Sterile disposable pipettes with appropriate calibration are used to transfer a blood sample from a container with EDTA capillary blood to DBS card. It's necessary to turn the EDTA container 20 times before sample transfer. All other stages of DBS preparation must be carried out in accordance with the procedure specified in the relevant SOPs. The survey site healthcare worker will be trained in accordance with the CDC's instructions for this procedure; his/her competence will be checked by the national coordinator. The DBS cards are identified by a survey identification number and dried on a grid at room temperature at the testing sites. After drying, the cards are packed into hermetically sealed packages, along with the humidity indicator and the dryer, and forwarded to the Reference Laboratory for HIV/AIDS diagnostic (each new batch is forwarded in 10 days) by a transport service that guarantees the appropriate temperature conditions.

All test results are entered into the Test Results Form (Annex 15. Test Results Form).

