8.7 Laboratory testing

All DBS samples are tested for recent infection and viral load (VL) in the Reference Laboratory for HIV/AIDS diagnostic in accordance with the testing algorithm and SOPs (Annex 24. Form of routine forwarding of the DBS samples to the Reference Laboratory).

Results of confirmed recency test will not be returned to patients. Results of VL will be returned by the lab to each site coordinator, who in turn will hand them over to local HIV clinics to which participants will be redirected. A medical specialist informs participants about the possibility of obtaining their results after they have been processed by the laboratory and received by the HIV clinics.

The quality of DBS cards is checked before testing (Annex 22. Form of rejected DBS registration). The cards are not tested if: there is a blood clot on a paper; blood is applied on both paper sides; insufficient amount of blood to cover the circles with 15 mm diameter; blood from different circles merged into one spot; serum separated from thrombocytes on a paper and created light circles around them; blood spots are blurred and not-colored; samples were not dried completely before transportation (intensive red spots); there are signs of rotting and mycotic DBS damage.

All HIV-positive DBS samples are tested as to recent infection (Maxim HIV-1 EIA Lag-Avidity EIA for Dried Blood Spots) and viral load (Abbott Real Time HIV-1 Test). Samples with $VL \geq 1000$ copies/ml are considered to be the confirmed cases of recent HIV-1 infection. Samples with $VL \leq 1000$ copies/ml are classified as long-term infection.

If the test is not performed correctly, an additional test is performed using the already collected sample (in a tube with anticoagulant). Additional blood is not collected. All residual samples are disposed of as corresponding category B in accordance with the order of the Ministry of Health of Ukraine dated June 9, 2022 No. 1602 On approval of changes to the State Sanitary and Epidemiological Rules and Norms for the Management of Medical Waste (<https://zakon.rada.gov.ua/laws/show/z1387-22#Text>)

All samples are destroyed and not used for future testing.

As of December 2020, RTI (i.e., HIV recency tests) have not been pre-qualified by the World Health Organization or approved by the U.S. Food and Drug Administration (FDA) for clinical use and are being used primarily for surveillance."

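### The cascade in 9.6 puts self-reported awareness and ART beside laboratory suppression without a common denominator, and does not use measured viral load to correct undisclosed status or treatment

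*Protocol*

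**What the plan says.** Section 9.6 of the protocol lists five cascade indicators. The first, the number of PWID living with HIV, is the population size estimate times survey prevalence. The next three are self-reported:

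- Awareness: "The proportion of PWID who self-reported their HIV-positive status during survey".
- Registration with an HIV clinic: also self-report.
- ART: "The proportion of PWID who self-reported receiving ART".

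All three are taken "among those who received HIV-positive rapid test result upon survey and agreed to answer questions about their experience of previous HIV-testing". All three are also to be compared with the healthcare worker's form; for awareness the text reads "This calculation will be cross-checked with the healthcare" worker's forms. No rule says what happens to a participant when the two sources disagree.

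The fifth indicator, suppression, is defined only as "Results of viral load testing carried out at the stage of laboratory analysis". It has no denominator, no threshold and no condition of having answered any question.

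Other sections show who has a viral load. Under 8.6, dried blood spots are prepared for each participant "with positive results of the third HIV rapid test", whatever was said in the interview, and also for a random 10% of those negative on the first test and for anyone who reports ART. Section 8.7 states "All HIV-positive DBS samples are tested as to recent infection" and, in the same sentence, for viral load. Section 4.3 describes "viral suppression, where effective sample is limited to the HIV positive fraction".

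**The concern.** The treatment cascade is a stated objective (section 3.0), and section 13.1 intends the data for monitoring the 95-95-95 goals. Reading the steps against one another requires the same people underneath each of them. In 9.6 three steps exclude HIV-positive participants who declined the testing-history questions, and the suppression step appears to include them.

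The second problem concerns people who do answer. Someone who knows their status or takes ART but denies it is counted as unaware or untreated. If that person's viral load is suppressed, the survey already holds objective evidence that points the other way, and section 9.6 makes no use of it. At stake are understated awareness and ART coverage, and a cascade that may point to gaps in testing or treatment that are partly gaps in disclosure.

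**Working it through.** **1. Which denominator does suppression use?** Section 9.6 does not say, so the sample-size calculation in 4.4 is the best evidence. Its inputs are suppression 44%, half-width 7 points, design effect 3.0, HIV prevalence 21%, 5% missing data and type I error 0.05.

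- Simple random sample of HIV-positive participants: 1.96² × 0.44 × 0.56 / 0.07² = 193.2
- With the design effect: 193.2 × 3 = 579.5
- Divided by prevalence: 579.5 / 0.21 = 2759.6
- Divided by (1 − 0.05): 2759.6 / 0.95 = 2905

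Rounding up at each step gives 2918. The protocol states 2914, so its figure is reproduced to within rounding. The only conversion from HIV-positive participants to the whole sample is the 21% prevalence. No factor allows for agreeing to answer, so suppression was sized as a share of all HIV-positive participants.

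**2. The steps side by side.**

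| Step in 9.6 | Source | Denominator |
|---|---|---|
| Living with HIV | size estimate × prevalence | all HIV-positive |
| Aware, registered, on ART | self-report, compared with a form | HIV-positive who agreed to answer |
| Suppressed | laboratory | not stated; by 4.3, 4.4 and 8.6 apparently all HIV-positive |

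Section 4.2 makes consent to every survey component an entry condition. The two groups can therefore differ only through refusal of individual questions, which section 14.4 allows.

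**3. Effect of refusal.** The protocol gives no refusal rate. Assume 60% awareness among those who answer and a declining share r. Awareness among all HIV-positive participants then lies between 0.60 × (1 − r), if no decliner is aware, and 0.60 × (1 − r) + r, if all are.

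- r = 5%: 57.0% to 62.0%
- r = 10%: 54.0% to 64.0%
- r = 20%: 48.0% to 68.0%

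The bounds lie on both sides of 60%, so refusal alone has no known direction.

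**4. Effect of non-disclosure by people who answer.** Let d be the share of suppressed participants who do not report ART (assumed; the protocol gives none). The shortfall in ART, in points of all HIV-positive participants, is 0.44 × d.

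- d = 5%: 0.44 × 0.05 = 2.2 points
- d = 10%: 0.44 × 0.10 = 4.4 points
- d = 20%: 0.44 × 0.20 = 8.8 points

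For scale, the planned half-width for suppression is 7 points. The shortfall equals it at d = 7/44 = 16%. Awareness falls by the same amount only if those who hide ART also hide their status; 9.6 treats these as separate indicators.

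**5. The base figure.** The 44% is itself uncertain. For the five sentinel cities with 2020 data, the table in 4.4 shows suppression of 68.8% to 90.9%, and the annex on city selection shows 20.0% to 62.1% (Kyiv 86.0% against 39.6%). Different denominators would be one explanation, but the protocol does not give a reason. With the annex extremes, d = 10% gives 0.200 × 0.10 = 2.0 to 0.621 × 0.10 = 6.2 points.

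**The case against.** The strongest reply is that the mismatch is read from silence. The suppression row fixes no denominator, and that detail, like any biomarker correction, could sit in an analysis plan that is not shown. This stands in part: 9.6 does not state a conflicting denominator. It does, however, fix the other three rows as self-report in a restricted group. Section 13.2 describes ART coverage for international reporting as a share of HIV-positive PWID, without that restriction.

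Second, the comparison with the healthcare worker's form is a safeguard. A reader might infer that the form merely repeats what the participant says. The form is not shown, so that cannot be claimed. What can be said is that no reclassification rule is attached and viral load is not named in the check.

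Third, the denominator gap may be small, since it arises only from refused questions. That stands.

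Two stronger readings are tempting. One is that every part of this problem lowers awareness and ART. Refusal does not, as the two-sided bounds show. The other is that suppression among the treated is overstated and could exceed 100%. With self-reported ART assumed at 55%, dividing aggregates gives 0.44/0.55 = 80%, against 0.44/(0.55 + 0.044) = 74% and 0.44/(0.55 + 0.088) = 69% after correcting 10% and 20% non-disclosure. But 9.6 specifies no such ratio, and the acronym list describes the components as linked for each respondent. If suppression is taken among those who reported ART, using their own viral load, hidden cases enter neither side and the ratio cannot pass 100%.

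Finally, trends matter: section 4.3 ranks them at least level with point estimates. Replacing self-report outright could break comparability if earlier rounds used it. That stands and shapes the remedy.

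**Conclusion.** The point holds as a weakness in the stated method. As 9.6 is written, the cascade steps need not share a denominator, and suppressed participants who answer but hide a known status or ART are counted as unaware or untreated. That error lowers awareness and ART; refusal adds an error of unknown sign.

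The size cannot be fixed from the protocol. An ART shortfall of 2.2-8.8 points rests on the 44% planning value and on an assumed 5-20% of suppressed participants not reporting ART. The same figure for awareness needs the further assumption that they also conceal their status. The net error of self-report is not established either, since the protocol gives no information on people who claim ART without taking it.

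**What to change.** In section 9.6:

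1. Use all participants with a confirmed HIV-positive result (three positive rapid tests under 8.5) as the denominator for every step.
2. Report how many declined the status and treatment questions, and how many have no valid viral load. Section 8.7 lists several grounds for rejecting a blood spot untested.
3. State the suppression threshold. The 1000 copies/ml cut-off in 8.7 is a rule for classifying recent infection, and 13.1 speaks of undetectable viral load; neither is tied to this indicator.
4. Present two cascades side by side: the self-report cascade, kept for comparison with earlier rounds, and a viral-load-adjusted one. In the adjusted cascade, HIV-positive participants with suppressed viral load who did not report status or ART are classed as aware and on ART, for analysis only.

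The cost is analysis wording; no new data are needed. A few people with naturally low viral load would be misclassified as treated, the adjustment cannot recover non-disclosers whose viral load is not suppressed, and trend analyses must use the self-report version.

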10.0 POPULATION SIZE ESTIMATION

Three methods will be used population size estimation (PSE) of PWID in selected cities using the IBBS 2023 data: multiplier, “capture-recapture” and successive sampling methods.

10.1 Multiplier method

The multiplier method is based on availability of at least two overlapping data sources specific to the population of interest, one being a count or registry of unique individuals belonging to the population, and another one being a representative survey that assessed whether the participants are present in the first data source. The data sources have to be independent of each other; define the target group in the same way; present the same time period, age and target group geography; be of sufficient data quality.

The formula to calculate the population size using the multiplier method is: $N = M/P$, Where:

N = Estimated Size

P = Proportion of survey participants who reported belonging to the registry (receiving the service, the object, or participating in the survey).

M = Number of individuals in the registry.

The 95% confidence intervals for proportions calculated for descriptive statistics using bootstrapping method with RDS weights will be used to calculate the lower- and upper limits for the population estimates.

The following data sources and indicators will be used for the multiplier method:

#	PSE indicator	Questionnaire item	Existing registry	Data provider
1	Registration in drug treatment clinics	Are you registered with the state narcological clinic in connection with drugs abuse or addiction?	Currently undetermined. Previously: Reporting form No.11 "Report on the morbidity of individuals with mental and behavioral disorders due to psychoactive substance use", annual. Table 2120 "Number of individuals with mental disorders due to intravenous drug use". Indicator: "among people under the supervision at the end of the reporting period".	Regional and city state drug treatment clinics.
2	Substance use treatment	Were you getting treatment in the state narcological clinic in 2022? (in-patient treatment / out-patient treatment) Have you been getting treatment in the state narcological clinic in 2023 (January-March)? (in-patient treatment / out-patient treatment)	Currently undetermined. Previously: Reporting form No.11 "Report on morbidity of individuals with mental and behavioral disorders due to psychoactive substance use", annual. Table 2300 "Composition of individuals in a drug treatment in-patient clinic". Indicator: "Mental and behavioral disorders due to the use of opioids, cannabinoids, cocaine, hallucinogens, combinations of several drugs and other psychoactive substances, total" Currently undetermined. Previously: Form No.11 "Report on the morbidity of individuals with mental and behavioral disorders due to psychoactive substance use", annual. Table 2100 "Contingent and treatment of individuals with mental disorders due to psychoactive substance use". Indicator: "Mental and behavioral disorders due to opioid use – covered with in-patient/out-patient treatment". Includes data on the number of people registered with a substance abuse clinic, who have already completed in-patient treatment at the end of the reporting period, including those, who have been treated at day drug treatment in-patient clinics.	Regional and city state drug treatment clinics.
3	Criminal	Have you been detained by the police in 2022?	Number of people notified of suspicion under articles	Statistical data

	prosecution	Have you been detained by the police in 2023?	307 and/or 309 during 2019 and 2023. Identified people who committed criminal offences under articles 307 and/or 309 during 2022 and 2023. Committed criminal offences under the influence of drugs, toxic and psychotropic substances under articles 307 and/or 309 during 2022 and 2023.	of the city police and the prosecutor's office.
4	Medications for opioid use disorder (MOUD) coverage	Have you received methadone or buprenorphine within the MOUD program in 2022? Are you taking methadone or buprenorphine within the MOUD program (January-March 2023)?	Number of people who were receiving MOUD in all city medical facilities during 2022. Number of people who were receiving MOUD in all city medical facilities during January-March 2023.	Public Health Center
5	Harm reduction coverage	Are you a client of any NGO working with people who inject drugs (have a client's card or an individual code)? Have you received free sterile needles/syringes from a non-governmental organization within the last 12 months (March 2022-March 2023)? Have you received free condoms from a non-governmental organization within the last 12 months (March 2022-March 2023)? Have you received HIV testing services from a non-governmental organization within the last 12 months (March 2022-March 2023)?	Number of PWID who received any harm reduction services in March 2022-March 2023.	SYREX database
6	Needle and syringe program coverage	Have you received sterile needles/syringes from a non-governmental organization within the last 3 months (January-March 2023)?	Number of PWID who have received syringes/needles within NGO network (average indicator for 3 months).	SYREX database
7	Condom programming coverage	Have you received condoms from a non-governmental organization within the last 3 months (January-March 2023)?	Number of PWID who have received condoms within NGO network (average indicator for 3 months).	SYREX database
8	HIV testing coverage	Were you tested with a rapid test for HIV in non-governmental organization in 2022? Were you tested with a rapid test for HIV in non-governmental organization in 2023 (January-March)?	Number of PWID who have been tested with the HIV rapid tests for 2022 and 2023 (separately for each year).	SYREX database
9	HCV testing	Did you get a rapid test for hepatitis C at NGO	Number of PWID who have been tested with the HCV	SYREX

	coverage	in 2022? Did you get a rapid test for hepatitis C at NGO in 2023 (January-March)?	rapid tests for 2022 and 2023 (separately for each year).	database
10	HBV testing coverage	Did you get a rapid test for hepatitis B at NGO in 2022? Did you get a rapid test for hepatitis B at NGO in 2023 (January-March)?	Number of PWID who have been tested with the HBV rapid tests for 2022 and 2023 (separately for each year).	SYREX database
11	Syphilis testing coverage	Did you get a rapid test for syphilis at NGO in 2022? Did you get a rapid test for syphilis at NGO in 2023 (January-March)?	Number of PWID who have been tested with the syphilis rapid tests for 2022 and 2023 (separately for each year).	SYREX database

These data will be collected for both IBBS and non-IBBS regions, to enable extrapolation of estimates.

* Considering the continued process of transition of harm reduction funding from international sources to the government, and potential changes in client counting approach, all service coverage indicators will be carefully examined for consistency of trends at the city level. In case of any rapid changes (particularly increases), additional data verification will be done, which will include cross-checking of reports and source documentation, and in-depth interviews with service providers. If any evidence of double counting will be identified, a correction coefficient will be proposed for these indicators.

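### The previously used drug-clinic registries listed for rows 1 and 2 of section 10.1 do not cover the group asked about in the survey; if reused, the all-substances in-patient total inflates the size estimate.

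*Protocol*

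**What the plan says.** Section 10.1 of the protocol defines the multiplier estimate as N = M/P. M is the registry count and P is the "Proportion of survey participants who reported belonging to the registry". Among the conditions it sets is that the two sources "define the target group in the same way".

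Rows 1 and 2 of the indicator table rely on drug treatment clinics:

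- **Row 1, registration.** The item is "Are you registered with the state narcological clinic in connection with drugs abuse or addiction". The registry is Table 2120, "Number of individuals with mental disorders due to intravenous drug use".
- **Row 2, treatment, first table.** The item is "Were you getting treatment in the state narcological clinic in 2022", with in-patient and out-patient answers and a parallel item for early 2023. It names no substance. The registry is Table 2300, for in-patients: "Mental and behavioral disorders due to the use of opioids, cannabinoids, cocaine, hallucinogens, combinations of several drugs and other psychoactive substances, total".
- **Row 2, treatment, second table.** The item is the same. The registry is Table 2100, "Mental and behavioral disorders due to opioid use", covered with in-patient or out-patient treatment.

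These sources are not fixed for 2023. The cells open with "Currently undetermined. Previously: Reporting form No.11" or a near-identical phrase.

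Section 4.2 admits only people who injected in the last 30 days, whatever the drug. Section 6.3 asks for at least one seed who injects stimulants.

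**The concern.** M/P estimates the number of people who inject drugs (PWID) only if M counts the same people that P describes. The three listed tables cover three different groups: intravenous use, all substances by any route, and opioids by any route. The row 1 item refers to drugs in general, the row 2 items name no substance, and no adjustment for drug group or route is described.

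Rows 1 to 4 are the multiplier sources outside the NGO client database that supplies rows 5 to 11. An error of definition in them therefore weakens the part of the multiplier evidence that does not depend on NGO counts. The resulting city sizes are used for weighting in sections 9.2 and 9.4, and the registry data are also collected for extrapolation to other regions.

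**Working it through.** The protocol gives no registry count, proportion or size estimate for these rows, so there is no figure to reproduce. What can be derived is the ratio of the expected estimate to the true size.

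Let N be the true number of PWID and T the number of them treated (or registered) as the item asks. Then P = T/N, and the estimate is M/P = N × (M/T). The ratio to the truth is M/T.

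**Table 2300 (all substances, in-patients).** If a share s of those counted are current PWID, then T = sM and the ratio is 1/s. The protocol does not give s. Assumed values:

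| s | 1/s |
|---|---|
| 0.9 | 1.11 |
| 0.8 | 1.25 |
| 0.7 | 1.43 |
| 0.5 | 2.00 |

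From the drug group and route alone, this ratio cannot fall below 1.

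**Table 2100 (opioids only).** Let o be the share of treated PWID who are treated for opioids, and f the share of this registry who are not current PWID. Then M(1 − f) = oT, and the ratio is o/(1 − f).

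Section 2.0 allows a rough value for o. It puts about 18,000 patients on medication for opioid use disorder at about 7% of people who inject opioids, and the PWID population at 350,500:

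- 18,000 / 0.07 = 257,143
- 257,143 / 350,500 = 0.734

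With o = 0.734:

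| f (assumed) | o/(1 − f) |
|---|---|
| 0 | 0.73 |
| 0.2 | 0.92 |
| 0.266 | 1.00 |
| 0.4 | 1.22 |

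The estimate is low only while fewer than about 27% of the registry are not current PWID. Above that it is high.

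**The two row 2 estimates against each other.** Suppose the share of non-PWID is the same in both tables, so s = 1 − f. Then (1/s) / (o/(1 − f)) = 1/o = 1/0.734 = 1.36, whatever that share is. If the stated 7% stands for anything from 6.5% to 7.5%, o runs from 0.79 to 0.685 and the gap from 1.27 to 1.46.

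**Table 2120 (intravenous use).** Let v be the share of registered PWID who are listed under intravenous use, and g the share of this registry who are not current PWID. The ratio is v/(1 − g). With v assumed at 0.9, it is 0.90 at g = 0, 1.00 at g = 0.1 and 1.29 at g = 0.3. The sign is open.

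**Would later steps catch this?** Section 10.4.1 drops estimates below NGO coverage or above 4% of adults. Section 2.0 reports that needle and syringe coverage reached 60% and has been maintained. If NGO coverage is near that level, the floor is about 0.6 of the truth, and an estimate at 0.73 passes. The correction coefficient in section 10.1 deals with double counting only. The anchored multiplier in section 10.4.2 gives more weight to narrow intervals, but section 10.1 builds those intervals from the uncertainty in P. An error in what M covers does not widen them.

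**The case against.** The strongest reply is that the plan does not commit to these tables. All three are recorded as past sources, and the matching condition in section 10.1 would govern the 2023 choice. This stands in part: the point is conditional on reuse. It does not remove the problem. The survey items are stated, P cannot be collected again after fieldwork, and no other registry definition is offered.

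A reader might infer that the tables bias the estimates in opposite directions by definition. The documents do not support that. Only Table 2300 has a direction that follows from its definition; Tables 2100 and 2120 can err either way. A reader might also combine 1.25 to 2.0 with 0.73 and report a 1.7- to 2.7-fold gap within row 2. That counts non-injectors in one table and none in the other, although neither is restricted to injecting.

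Three further replies carry weight:

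- Separate in-patient and out-patient answers can be combined to suit a registry, so treatment setting is not a shown mismatch.
- Police data, the opioid medication programme, capture-recapture and successive sampling also stand outside the NGO database. With the range check and triangulation, they limit the damage from one discordant row, though a moderate bias can survive.
- Section 7.4 keeps the core questionnaire stable for trends, so rewording the existing items would have a cost.

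**Conclusion.** The point holds as a conditional one. The listed clinic registries do not meet the protocol's own matching condition.

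- **Table 2300**, if reused unchanged, inflates the estimate by 1/s: 1.25 to 2.0 times for an assumed injector share of 0.8 to 0.5.
- **Table 2100** has a net bias of unknown sign.
- **The two row 2 estimates** would differ about 1.36-fold from definitions alone. This assumes equal non-injecting shares in both tables and that treated PWID have the same drug mix as all PWID. The 73% opioid share behind it is approximate, because it sets a mid-2022 figure against a 2017 population size.
- **Row 1** is a milder mismatch of unknown sign.

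No stated figure in the protocol is wrong on this account, because none is given.

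**What to change.** Before fieldwork, and when the 2023 registries are chosen:

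1. Do not use the all-substances in-patient total as M unless the clinics can restrict it to injecting drug use.
2. Keep the existing items for trend comparison. Add a short follow-up asking for which substance the participant was treated or registered, so that P can be limited to the group the registry covers. For Table 2100, that means counting only treatment for opioid use.
3. Ask for the injecting restriction on Table 2100 as well. Limiting P to opioid treatment repairs the drug group but leaves a ratio of 1/(1 − f) from people in M who are not current PWID.
4. State in section 10.4 that a row whose registry and item cannot be matched is left out of the city consensus.

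The cost is one or two added questionnaire items and a more specific data request. The protocol does not show whether clinics can supply counts by injecting status, so one or two of the eleven indicators may have to be dropped.
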